2.3.2 Benefit Assessment

As noted in Section 2.2.1, AML is a progressive and fatal condition for the majority of subjects. Though long-term remission can result from first-line therapy, treatment for persistent or recurrent disease is given to slow progression or reduce symptoms. Typical symptoms arise from impaired bone marrow function, and include poor coagulation, anemia, and susceptibility to infection. Most subjects will have persistent or relapsing disease, and the 5-year survival for all diagnosed patients is < 30% (SEER Program, 2020). In ALL and non-Hodgkin's lymphoma (NHL), targeted cell therapies have led to remarkable results, even for patients with refractory and advanced disease. The potential benefit of NTLA-5001 is as an immunotherapy agent with activity similar to existing targeted cell therapies for ALL and NHL, leading to reduction in disease burden and prolongation of life through killing of AML cells expressing WT1, which is at 10- to 100-fold the level seen on normal tissues.

In this study, NTLA-5001 activity on AML will be evaluated by serial disease assessments including bone marrow sampling, as well as clinically by time to disease progression, survival, and quality of life (QOL). It is expected that, based on the starting dose of [REDACTED] cells, planned dose escalation regimen, and the known potential risks of therapy, that an optimal biologically active dose will be identified in this study.

2.3.3 Overall Benefit: Risk Conclusion

The therapeutic hypothesis supporting the development of NTLA-5001 in AML has been clinically validated using cell therapy for other hematologic malignancies.

As no clinical trials of NTLA-5001 have been conducted in humans, the initial patient population being studied consists of subjects who have persistent or recurrent disease despite use of approved therapy. The selection of this subset of subjects with AML seeks to optimally balance risk and potential benefit in this first clinical evaluation of a new therapy, consistent with the established guiding principles set out in various regional and national guidelines on first-in-human clinical studies. As clinical studies in humans have not yet been conducted with NTLA-5001, all potential side effects are not yet known. As part of the risk mitigation strategy, potential risks for each subject will be monitored via a multifaceted approach, including adverse event (AE) monitoring and safety laboratory evaluations. Dose level changes for subsequent cohorts will be made after review of all data with investigators, and dose selection for the safety expansion cohort will be done in conjunction with the investigators and DMC.

3 STUDY OBJECTIVES AND ENDPOINTS

OBJECTIVES	ENDPOINTS
Primary	

 • Dose escalation: To identify dose for use in the expansion cohorts 	
 • safety and tolerability as determined by AEs

 • Dose expansion: To evaluate the safety and tolerability of NTLA-5001 in subjects with AML and blasts <5% of bone marrow (Arm 1) and in subjects with AML and blasts ≥5% of bone marrow (Arm 2) 	
 • dose-limiting toxicities (DLTs) (dose escalation only)
Secondary	

 • To characterize the cell kinetics (CK) of NTLA-5001 in peripheral blood 	
 • frequency and persistence of NTLA-5001 according to the TCR transgene copy number (via droplet digital polymerase chain reaction [ddPCR])

 • To estimate the anti-tumor activity of NTLA-5001 in subjects with AML 	
 • Disease response (including measurable residual disease [MRD] response), duration of response / remission, and disease progression (see Section 13.4)
Exploratory	

 • To estimate other cancer-related outcomes in subjects with AML 	
 • overall survival • Eastern Cooperative Oncology Group (ECOG) performance status • QOL as measured by the European Organization for Research and Treatment of Cancer Quality of Life Questionnaire (EORTC QLQ-C30) instrument and length of hospital stay after NTLA-5001 infusion

 • To characterize subject AAV exposure 	
 • presence of adenovirus vector in blood and urine

 • To characterize immunologic parameters and characteristics of NTLA-5001 cells after administration in subjects with AML 	
 • plasma cytokine levels • WT1 expression on tumor • NTLA-5001 characteristics including flow cytometry, phenotype, editing, and gene expression • bone marrow immune parameters and NTLA-5001 cell kinetics

4 STUDY DESIGN AND DOSE RATIONALE

4.1 Overall Study Design

This is Phase 1/2a, first-in-human, single-dose study to investigate NTLA-5001 in subjects with AML. The design is according to guidance for first-in-human trials and for the investigation of advanced therapy medicinal products, including the European Medicine Agency “Guideline on strategies to identify and mitigate risks for first-in-human and early clinical trials with investigational medicinal products”; and draft guidance “Guideline on quality, non-clinical and clinical requirements for investigational advanced therapy medicinal products in clinical trials”; and the FDA draft guidance “Acute Myeloid Leukemia: Developing Drugs and Biological Products for Treatment”. The design is to ensure the safety and well-being of trial subjects and to mitigate risk to the greatest extent possible.

This study consists of 2 phases: dose escalation and dose expansion. The dose escalation phase of the study will consist of up to 3 cohorts of subjects in Arm 1 and 3 cohorts of subjects in Arm 2. Each Arm 1 cohort will include up to 6 subjects, as detailed in dose escalation below. Each Arm 2 cohort will include 3 to 6 subjects. Once a dose is identified for detailed assessment of safety in Arm 1 subjects and 6 subjects have been enrolled at that dose, an expansion cohort will be opened for an additional 9 subjects in Arm 1. Once a dose is identified for detailed assessment of safety in Arm 2 subjects, a safety expansion cohort will be opened for an additional 9 subjects in Arm 2.

The screening period will be up to 28 days, and a subject that meets all inclusion and none of the exclusion criteria will be enrolled into the leukapheresis phase in Arm 1 for subjects with AML blasts <5% of bone marrow or in Arm 2 for subjects with AML blasts \geq 5% of bone marrow. During screening, MRD will be measured in bone marrow by central laboratory assessment. After study entry, subjects may have repeat BM assessment prior to Arm assignment based on whether screening biopsy was prior to study consent, interval since screening study, change in condition, or bridging therapy. If an Arm 1 subject is found to have \geq 5% bone marrow blasts at repeat BM assessment, the subject may be re-assigned to Arm 2 or, if Arm 2 is not yet enrolling subjects, the subject may receive NTLA-5001 at Dose Level -1.

Each subject will undergo leukapheresis for collection of peripheral blood mononuclear cells (PBMC). [REDACTED] After leukapheresis, subjects who meet criteria for treatment and who have manufactured NTLA-5001 that meet release requirements will enter the treatment phase for the administration of lymphodepleting chemotherapy and study medication. Subjects may receive bridging therapy between leukapheresis and treatment (see Section 6.1.3.2).

Each subject in the treatment group will receive lymphodepleting chemotherapy on Day -5, -4, and -3 (see Section 6.1.3.3). A subject will be administered a single dose of NTLA-5001 on Day 0. Subjects will be observed in hospital for a minimum of 7 days following dosing, and subjects must remain within 2 hours of the location of the trial site to receive any needed follow up assessments or care until Day 14. UK subjects will be observed in hospital for a minimum of 14 days following dosing. Additional visits will take place at Week 2, 4, 8, and 16, then at 12-week intervals through Week 112 or until the subject is no longer receiving clinical benefit.

Subjects who are no longer receiving clinical benefit will continue to be followed with clinic visits to assess subject survival and AEs every 12 weeks until 112 weeks after administration of NTLA-5001. After participating in this study, all subjects will be followed as part of a long-term monitoring program per local and national regulations. All subjects will be followed for a minimum of 5 years in the UK and for a minimum of 15 years in the US.

Infusion of NTLA-5001 that does not meet the intended dose or does not meet release criteria (as specified in the Cell Therapy Manual) will be considered for NTLA-5001 treatment with approval by the Sponsor and investigator, except in the UK. Such subjects who receive therapy will not be counted for filling a slot in the dose escalation cohort or safety expansion cohort. In the UK, a dose of NTLA-5001 manufactured for a patient that fails release criteria or is otherwise inadequate will not be given to a patient, and no subject at a UK site may begin lymphodepleting chemotherapy before the subject's product meets manufacturing release criteria.

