6.2.1.3 Dose Escalation and Dose Reduction Decisions

If none of the initial dose evaluation group subjects experience a DLT, subjects in the treatment phase who have not yet received NTLA-5001 and subsequent subjects entering the treatment phase will be eligible for the next dose escalation cohort.

If 1 of the initial dose evaluation group subjects experiences a DLT, enrollment will continue in the dose evaluation group for 3 additional subjects. When the last subject in the expanded dose evaluation group has been observed through Day 28:

- If no subject in the expanded dose evaluation group experiences a DLT, subjects in the treatment phase who have not yet received NTLA-5001 and subsequent subjects entering the treatment phase will be eligible for the next dose escalation cohort.
- If 1 or more additional subject in the expanded dose evaluation group experiences a DLT, no dose escalation will be proposed. Subjects in the treatment phase who have not yet received NTLA-5001 and subsequent subjects entering the treatment phase will be eligible for Dose Level -1 if DLTs are seen at Dose Level 1, or the next lower dose level will be declared the maximum tolerated dose (MTD), if DLTs are seen at Dose Level 2 or 3. Fewer than 2/6 subjects with DLTs will establish the MTD.

If 2 or 3 of the initial dose evaluation group experiences a DLT, no dose escalation will be proposed. Subjects in the treatment phase who have not yet received NTLA-5001 and subsequent subjects entering the treatment phase will be eligible for Dose Level -1 if DLTs are seen at Dose Level 1, or the next lower dose level will be expanded to 6 subjects if DLTs are seen at Dose Level 2 or 3. Fewer than 2/6 subjects with DLTs will establish the MTD.

If a dose escalation is proposed, the subsequent cohort dose may be reduced or increased by up to 50% if the Sponsor and investigator agree, based on observations in the prior cohort. At the Sponsor's discretion, up to 6 subjects may be enrolled in any dose cohort for Arm 1 or Arm 2.

If a subject receiving out-of-specification cells has a DLT, this finding would not be attributed to DLT tally for a specific Dose Level; but would be reviewed as part of the overall safety profile in conjunction with planned safety reviews and by the Sponsor, investigators, and DMC. The event would be considered when making dose escalation decisions, stopping rule decisions, and/or dose selection for expansion cohort.

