13.8 Appendix 8 Subject Accrual Order During Dose Escalation

Selected examples shown through dose selection in each Arm. Accrual of six subjects in cohorts prior to expansion is not shown. Each square represents 1 subject with dose level indicated by number. Symbol “*” indicates DLT. Symbol “•” indicates dose escalation decision.

1. No DLT observed

Arm 1	1	1	1	•	2	2	2	•	3	3	3			
Arm 2	1	1	1	•	2	2	2	•	3	3	3			

2. No DLT observed, Arm 1 accrual slower

Arm 1	1	1		•	2			•	3	3		3		
Arm 2	1	1	1	•	2	2	2	•	3	3	3			

3. Single DLT in Arm1, DL2

Arm 1	1	1	1	•	2	2	2*	2	2	2	•	3	3	3
Arm 2	1	1	1	•	2	2		2	•	3	3	3		

4. Single DLT in Arm1 DL2, Arm 1 accrual slower

Arm 1	1	1		•	2*	2	2	2	2	2	•	3		3	3
Arm 2	1	1	1	•	2	2	2	•	3	3	3				

5. Single DLT in Arm 2, DL2

Arm 1	1	1	1	•	2	2	2	•	3	3	3			
Arm 2	1	1	1	•	2	2*	2	2	2	2	•	3	3	3

6. MTD reached in Arm 1, DLT seen in 2/5 subjects at DL2†

Arm 1	1	1	1	•	2	2*	2	2	2*					
Arm 2	1	1	1	•	2		2	2						

7. MTD reached in Arm 2, DLT seen in 2/2 subjects at DL2

Arm 1	1	1	1	•	2	2	2	•	3	3	3			
Arm 2	1	1	1	•		2*	2*							

8. MTD reached in Arm 2, DLT seen in 2/3 subjects at DL2, Arm 1 accrual slower

Arm 1	1			•	2	2		2	•	3	3		3	
Arm 2	1	1	1	•	2*	2	2*							

† In Example #6 above, the MTD for subjects in Arm 1 is reached at a dose lower than the dose under evaluation in Arm 2. Accruing subjects in the order of Example #6 is not expected, because the risk of severe or serious adverse events after cell therapy is correlated with a subject’s tumor burden ([Garcia-Manero et al, 2015](#); [Garzon et al, 2017](#)). If, as in Example #6, the MTD for Arm 1 is reached at or below the dose under investigation in Arm 2, enrollment in Arm 2 will be paused and data reviewed by the Principal Investigators, Sponsor, and the DMC.

DL = dose level; DLT = dose-limiting toxicities; MTD = maximum tolerated dose

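### Arm 2 may open its nine-subject expansion on three DLT-free subjects where no MTD has been established, chiefly at Dose Level 3, because the six-subject condition is stated for Arm 1 only

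*Protocol*

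**What the plan says.** Protocol Section 4.1 gives the two expansion triggers in consecutive sentences. For Arm 1 the trigger is a dose identified "in Arm 1 subjects and 6 subjects have been enrolled at that dose, an expansion cohort will be opened". For Arm 2 it is "Once a dose is identified for detailed assessment of safety in Arm 2 subjects, a safety expansion cohort will be opened", with no number attached. The Synopsis and SAP 2.2 repeat the same pair.

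Cohort sizes also differ. For Arm 1, "Each Arm 1 cohort will include up to 6 subjects, as detailed in dose escalation below", so there is no minimum. For Arm 2, "Each Arm 2 cohort will include 3 to 6 subjects".

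Section 6.2.1.3 moves a 0/3 cohort on to the next dose level. Filling any cohort to six is left to the sponsor's discretion. The six-subject limit is tied to the MTD: "Fewer than 2/6 subjects with DLTs will establish the MTD". Section 6.2.2 has the DMC recommend a dose or range of doses and the sponsor decide. It sets no minimum number and does not require the chosen dose to be an MTD.

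Appendix 8 introduces its accrual diagrams with "Selected examples shown through dose selection in each Arm" and adds "Accrual of six subjects in cohorts prior to expansion is not shown". That note is not limited to one arm.

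**The concern.** Section 6.2.1.4 says that the risk of severe events after cell therapy rises with tumor burden. Arm 2 is the higher-burden arm, yet it has the weaker stated condition for expansion. In a first-in-human study, three subjects without a DLT are thin support for treating nine more at the same dose.

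DLTs are an endpoint in escalation only (Section 3). Events of DLT type among the nine would be recorded as adverse events, but no DLT limit would act on them. The pausing criteria in Section 6.2.1.5 cover part of the ground. For CRS, ICANS and organ toxicity they are narrower than the DLT list: Grade 3 ICANS is a DLT but does not pause enrollment. For GVHD, T cell proliferative disorder and treatment-related death they are broader.

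The Appendix 8 note reads as if six subjects come before expansion in both arms. Section 4.1 does not deliver that for Arm 2, so sites and the DMC could reasonably apply different rules.

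**Working it through.** **1. The plan's own total.** 2 arms × (3 cohorts × 6 + 9) = 2 × 27 = 54, matching the Synopsis. The maximum already allows six at every level in Arm 2.

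**2. When does an Arm 2 level reach six?** Reading Sections 6.2.1.3 and 6.2.2 case by case:

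| Situation | Six at the dose? |
|---|---|
| 1/3 at the level | Yes, three more are required |
| 0/3, then 2 or 3 of the first three at the next level have DLTs | Yes: "the next lower dose level will be expanded to 6 subjects if DLTs are seen at Dose Level 2 or 3" |
| 0/3, then 1/3 plus at least one more DLT at the next level | Lower level is declared the MTD; the sentence that follows points to six |
| 0/3, sponsor chooses to fill | Optional |
| 0/3 at a lower level, chosen although the level above did not fail | Not required |
| 0/3 at Dose Level 3 | Not required; no higher level exists to trigger a fill |

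The gap is the last two rows, and chiefly the last.

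**3. Size of the gap.** The documents give no DLT rate, so p from 10% to 50% is assumed, with independent subjects and Arm 2 data alone. Let q = 1 − p.

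- Permitted to clear as written (0/3, or 1/3 then 0/3): q³ + 3p·q⁵
- Clears with six required and fewer than two DLTs: q³·P(at most 1 of 3) + 3p·q⁵
- Difference: q³·P(at least 2 of 3)

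At p = 0.3, as written: 0.343 + 0.9 × 0.16807 = 0.494. With six required: 0.343 × 0.784 + 0.151 = 0.420. The difference is 0.343 × 0.216 = 0.074.

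| Assumed p | As written | Six required | Difference | Given 0/3, P(at least 2 of next 3) |
|---|---|---|---|---|
| 10% | 0.906 | 0.886 | 0.020 | 0.028 |
| 20% | 0.709 | 0.655 | 0.053 | 0.104 |
| 30% | 0.494 | 0.420 | 0.074 | 0.216 |
| 40% | 0.309 | 0.233 | 0.076 | 0.352 |
| 50% | 0.172 | 0.109 | 0.0625 | 0.500 |

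The largest difference is about 0.077, near p = 0.36.

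**4. Precision.** Exact one-sided 95% upper limits for the DLT rate are:

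- 0/3: 1 − 0.05^(1/3) = 63%
- 0/6: 1 − 0.05^(1/6) = 39%
- 1/6: 95th percentile of Beta(2, 5) = 58%

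The gain is large if the next three are clean and small if one has a DLT.

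**The case against.** The strongest reply is that the asymmetry has a sensible reason. Arm 1 cohorts have no minimum, and Appendix 8 Examples 2 and 8 show Arm 1 leaving a level after a single subject. A count is then needed in Arm 1 as a backfill, while Arm 2 always has at least three. This is plausible, and the documents neither confirm nor exclude it. A reader might infer that the Arm 2 count was dropped by mistake, but nothing in the text shows that. The gap stands whatever its cause.

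A reader might also infer that any Arm 2 dose at 0/3 goes straight to expansion. The documents do not support this. A 0/3 result leads to the next cohort. Expansion needs a dose to be selected after DMC review and a sponsor decision, and where an MTD is established the text already points to six. The as-written probabilities are therefore what the plan permits, not how often it would happen.

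Other safeguards are real: periodic DMC review of safety data (Synopsis, SAP 6.7), review of DLT data from both arms at each escalation decision (Section 6.2.1.1), and the pausing criteria. None of them sets a minimum number treated.

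Two further points are conceded. The Appendix 8 note is a caption rather than an operative rule, and it could refer to Arm 1 alone. The absence of a DLT limit during expansion applies to Arm 1 as well, so it adds to the consequence of the gap but is not itself a difference between the arms. Nor does any text make fewer than 2/6 a condition for expansion in Arm 1, which asks only that six be enrolled.

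**Conclusion.** The point holds in limited form. No operative text requires six Arm 2 subjects before expansion when the dose is chosen without establishing an MTD, and Dose Level 3 at 0/3 is the main case. The Appendix 8 note suggests that six was expected, without making it a rule.

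The numerical effect is modest: about 2 to 8 percentage points in the permitted chance of clearing. The conditional figure is closer to the decision the DMC would face. Once 0/3 is seen, about one in five doses with a true 30% rate, and about one in three at 40%, would breach the limit on the next three subjects. These figures rest on assumed rates, independence of DLTs, and Arm 2 data alone at a single level.

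The change is worth making because it is cheap and bears on subject safety. SAP Section 7 reports that only 2 subjects were treated before termination, so this concerns the plan and had no effect on the data.

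**What to change.** In Section 4.1 and the Synopsis, mirrored in SAP 2.2, state that the Arm 2 expansion opens only once six DLT-evaluable Arm 2 subjects have been treated at the chosen dose with fewer than two DLTs among them.

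If three is the intended minimum, say so. Then apply the DLT definition and the fewer-than-2/6 limit to the first Arm 2 expansion subjects until six at that dose are evaluable, and correct the Appendix 8 note so that it no longer implies six in both arms.

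Leave the Arm 1 condition as it is.

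Cost of the first option: one sentence in three places, and up to three more Arm 2 subjects at the dose before expansion (at most 6 + 9 = 15 there, against 3 + 9 = 12). The planned maximum stays at 54. Expansion may open later, by the time needed to accrue and observe the added subjects. The second option adds no subjects at the dose, but some expansion subjects would be treated before six are evaluable.

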4.1.1 Replacement of Subjects

An additional subject will be added to a dose cohort if a subject in that cohort does not receive a full dose of NTLA-5001 as per their assigned cohort or fails to complete Day 28 assessments. Any subject who experiences a DLT will be considered evaluable. Data for all subjects will be part of the safety dataset for reporting of the study.

4.1.2 Screen Failures

Screen failures are defined as subjects who consent to participate in the clinical study but are not subsequently dosed with NTLA-5001.

4.1.3 Dose Rationale

The first cohort of subjects in Arm 1 and in Arm 2 will receive [REDACTED]. The starting dose (Dose Level 1) was selected based on human trials of investigational TCR-T cell products that are similar in trial design due to the use of naturally occurring TCR (without affinity enhancement) and lymphodepleting chemotherapy. Dose Level 1 was chosen near the lower end of the range of recent precedents, due to nonclinical study results for NTLA-5001, suggesting the potential for increased TCR expression compared to products which do not eliminate expression of the native TCR (see Investigator's Brochure for additional detail). The dose escalation interval is similar to prior human TCR-T trials, and the highest dose (Dose Level 3) is lower than administered in several TCR-T cell product studies. Because NTLA-5001 is a cellular therapy product, it is administered via the IV route. NTLA-5001 is dosed as a single administration with the intent that cells will show long-term self-renewal after engraftment. At this time, there is no schedule proposed for re-administration of an additional dose.

4.2 End of Study

Subject Completion

A subject will be considered as having completed the study after completion of their Week 112 visit. Subjects who are no longer receiving clinical benefit will continue to be followed with clinic visits to assess safety every 12 weeks until 112 weeks after administration of NTLA-5001.

Subjects who are not receiving clinical benefit may receive additional treatment or supportive care per their Investigators for the duration of the study (see Schedule of Activities [SoA], Section 1.3).

Study Completion and Long-Term Follow-up

The study will be considered completed with the last visit by the last subject.

Early Discontinuation from Study (Early Termination)

All subjects enrolled in the study will be followed for 112 weeks unless a subject withdraws consent, is lost to follow-up, or has died. Subjects have the right to withdraw from the study at any time for any reason.

The Sponsor may terminate enrollment into the study, either in its entirety or at any study site, at any time. The study may then be terminated when the last subject dosed has been followed for 28 days. Regardless of the Sponsor's decision to terminate enrollment, those subjects who have received treatment with NTLA-5001 will continue to be followed in a long-term monitoring program needed to comply with local regulatory requirements/guidance for subjects administered a gene therapy. All subjects will be followed for a minimum of 5 years in the UK and for a minimum of 15 years in the US.

